#### 7.5.7.2 Best-corrected Near Visual Acuity

All the available monocular best-corrected near visual acuity at each protocol specified scheduled visit will be presented for the implanted eyes. The categorical presentations will include the visual acuity of 75 letters or better, 70 letters or better, 65 letters or better, 60 letters or better, 55 letters or better, 50 letters or better, 45 letters or better, 40 letters or better, and fewer than 40 letters.

## 7.5.7.3 MRSE Stability

The MRSE mean, standard deviation, median, minimum, and maximum will be calculated. The percentage of eyes will be calculated for MRSE within  $\pm 0.50$  D and  $\pm 1.00$  D.

## **7.5.7.4 Tonometry**

Goldmann measurements of IOP and its change from baseline will be summarized descriptively at each visit.

## 7.5.7.5 Slit Lamp, Gonioscopic and Fundus Examination Findings

Numbers and percentages of eyes will be summarized for each of the findings at each visit.

#### 7.5.7.6 Contrast Sensitivity (Mesopic)

Mesopic contrast sensitivity and its change from baseline will be summarized descriptively at each visit.

# 7.5.7.7 Optical Coherence Tomography (OCT)

Numbers and percentages of eyes will be summarized for each of the findings at each visit.

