5.1. Inclusion Criteria

- 1. Subjects aged 55 years or older.
- 2. Subjects who have already had cataract surgery with an Alcon SN60WF, SA60AT or SA60WF monofocal intraocular lens with a lens power between 17.0 diopters and 24.0 diopters clearly evidenced by photographic documentation by one of the following:
 - patient medical record
 - clinic chart with labeling attached
 - surgical record with labeling attached, or
 - patient identification card with make, model and serial number.
- 3. Subjects who have already had cataract surgery at least 6 months from the planned date of the IOPCL surgery.
- 4. Subjects with non-neovascular dry AMD or stable wet AMD meeting the following criteria:
 - No macular fluid retention in the past 12 months
 - No treatment within the past 12 months
 - No change in Amsler Grid test within the past 12 months
 - No subretinal fluid or macular hemorrhage confirmed by optical coherence tomography (OCT) imaging.
 - No fundoscopic changes within the past 12 months (i.e., changes in retinal pigment epithelium).
- 5. Subjects with best corrected distance visual acuity from 20/80 to 20/800.
- 6. Subjects with a preoperative manifest refraction spherical equivalent (MRSE) of +1.0D to -1.0D.
- 7. Subjects with ≤1.0D of corneal cylinder determined by keratometry readings.
- 8. Subjects who are unsatisfied with their current near vision correction provided by either spectacles or external magnifier.
- 9. Subjects who have experienced and failed one or more high-magnification refractive correction alternatives to the IOPCL AMD-MAG.

- 10. Subjects who demonstrate at least 10 letters of near visual acuity improvement with the simulation/tolerance test (using manifest refraction with +7.0D add) compared to conventional near vision testing (using manifest refraction with +3.0D add).
- 11. Subjects with a minimum endothelial cell count of 1800 cells/mm².
- 12. Subjects willing to abstain from pursuing any other surgical vision-correcting procedures for the duration of the study.
- 13. Subjects who are willing and able to complete all required postoperative visits.
- 14. Subjects who are able to comprehend and sign a statement of informed consent.

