# 6.2 Sample Size

Sample size is limited to maximum of 10 subjects (eyes) for this Early Feasibility Study (EFS).

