# 7.5.7.8 Specular Microscopy

Endothelial cell count and its change from baseline will be summarized descriptively at each visit.

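### OCT and fundus findings are planned as by-visit counts with no within-eye comparison to baseline, so worsening and offsetting changes can go unseen in these tables

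*SAP*

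**What the plan says.** SAP 7.5.7.7 deals with OCT in a single sentence: "Numbers and percentages of eyes will be summarized for each of the findings at each visit". SAP 7.5.7.5 repeats that sentence for slit lamp, gonioscopy and fundus. Neither section mentions change from baseline, a shift table, a grade or a listing of eyes.

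The neighbouring sections do use the preoperative value. For pressure: "Goldmann measurements of IOP and its change from baseline will be summarized descriptively at each visit". For contrast sensitivity: "Mesopic contrast sensitivity and its change from baseline will be summarized descriptively at each visit". For specular microscopy: "Endothelial cell count and its change from baseline will be summarized descriptively at each visit". SAP 7.5.7.9 also plans change from the preoperative VFQ-25 score, and SAP 7.5.3 plans a line listing for secondary surgical interventions.

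Protocol 15 schedules OCT preoperatively and at 30-60, 120-180 and 330-420 days. Dilated fundoscopy has the same visits plus 7-14 days. Slit lamp is also done preoperatively; gonioscopy is not.

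On the population, inclusion criterion 4 of Protocol 5.1 admits "Subjects with non-neovascular dry AMD or stable wet AMD meeting the following criteria". Those criteria include "No subretinal fluid or macular hemorrhage confirmed by optical coherence tomography (OCT) imaging" and 12 months without fundoscopic change. Protocol 7 has a co-managing retinal specialist follow retinal status during the trial.

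**The concern.** The study has one arm and no masking (SAP 6.3), so an eye's own preoperative state is the only reference for judging change after the implant. A count of eyes with a finding at each visit does not use that reference eye by eye.

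Two things can be lost. First, every eye enters with macular disease, so some macular findings will already be present; a present/absent count does not move when such a finding gets worse. Second, where a finding is present in some eyes and not others, one eye can acquire it while another loses it, and the count stays level.

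The protocol treats retinal stability as important, both in its entry criteria and in its use of a retinal specialist. A table that can read as stable while individual eyes have changed serves that interest poorly, both in the final report and in the 4-6 month interim analysis (SAP 6.8).

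**Working it through.** There is no planned figure to reproduce: these analyses are descriptive, and 10 eyes is a stated maximum rather than the result of a calculation (SAP 6.2). The check asks how much the planned counts reveal about change within eyes. The baseline counts below are illustrative; the documents give none.

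**Setup.** Let n = 10 eyes, all seen at both visits. Let a be the number with a finding preoperatively, b the number with it at a later visit, and x the number of new eyes (absent, then present).

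- Eyes with the finding both times number b − x, which must lie between 0 and a. So x ≥ b − a and x ≤ b.
- New eyes come from those without the finding at entry, so x ≤ n − a.
- Hence x lies between max(0, b − a) and min(b, n − a).
- Any of the b − x eyes with the finding both times may have worsened. So the number of new-or-worsened eyes lies between max(0, b − a) and b.

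| Preoperative | Later visit | New eyes | New or worsened eyes |
|---|---|---|---|
| 0/10 | 2/10 | exactly 2 | exactly 2 |
| 2/10 | 2/10 | 0 to 2 | 0 to 2 |
| 5/10 | 5/10 | 0 to 5 | 0 to 5 |
| 5/10 | 8/10 | 3 to 5 | 3 to 8 |
| 8/10 | 8/10 | 0 to 2 | 0 to 8 |
| 10/10 | 10/10 | exactly 0 | 0 to 10 |

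**Reading the table.**

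- First row: a finding absent from every eye at entry is fully visible when it appears. Subretinal fluid and macular hemorrhage, which criterion 4 requires to be absent, are of this kind.
- Middle rows: the counts fix the number of new eyes only to a range.
- Last row: no eye can be new, and worsening in anything from none to all of the eyes gives the same 10/10, provided the form records presence only.

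**Missed visits.** SAP 6.5 uses available data without imputation, so the eyes behind the two percentages can differ. Suppose 5/10 have a finding preoperatively, two eyes are then missed, and 7/8 have it. The number positive at entry among the eight seen could be 3, 4 or 5. The formula with n = 8 then gives 4 to 5, 3 to 4, or 2 to 3 new eyes, so 2 to 5 overall. Pairing within eye removes this ambiguity among the eyes seen.

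**What pairing gives.** A preoperative-by-visit cross-tabulation replaces each range of new eyes with one exact number. Showing worsening also needs grade, extent or a better/same/worse entry for each finding.

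**The case against.** The strongest case against is that the plan has other routes to the same information, and most of that stands.

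- **Adverse events.** Protocol 17 sends any adverse experience the investigator observes to the adverse event form, whatever the attribution. Protocol 16.3 names macular edema, cystoid macular edema and retinal detachment, and many anterior-segment findings such as iritis, iris chafing and pigment dispersion. SAP 7.5.6 reports each event by visit, cumulatively and as persistent. A reader might infer that by-visit counts are the only report of retinal and slit-lamp findings; they are not. The limit is that AMD progression is not named. It would have to enter under Other, at the investigator's discretion, or through a named event such as edema.
- **Acuity.** SAP 7.5.1 and 7.5.2 count eyes losing 10 or more letters from preoperative, which is a within-eye analysis. It would register a large functional loss, but not structural change with a smaller loss.
- **New findings.** A reader might infer that no new finding shows in these tables. The 0/10 then 2/10 row refutes that.
- **Slit lamp.** A reader might carry the argument from AMD at entry over to slit lamp. It does not transfer: macular disease gives no reason to expect anterior-segment findings at baseline, and several exclusions in Protocol 5.2 make some of them less likely. Only the cancellation argument applies there.
- **Unseen forms.** A reader might infer that macular percentages must sit near 100% at every visit. Entry mixes dry and stable wet AMD, so an individual finding need not be present in every eye. The list of findings and any grading belong to the clinical methods and case report form appendices, which are not in the text reviewed. If the forms already code grade or change, by-visit counts would show some of it.
- **Neighbouring sections.** Pressure, contrast sensitivity and cell count are numeric, so a mean change comes naturally; counts for categorical findings follow SAP 6.1. The contrast is not an internal contradiction. It shows only that baseline comparison is used elsewhere and could be used here.

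**Conclusion.** The point holds for OCT and fundus findings. The planned summaries make no within-eye comparison with the preoperative examination, although that examination is scheduled. They cannot show worsening of an AMD finding present at entry if only presence is recorded, and they can hide offsetting changes: equal counts of 5/10 are compatible with 0 to 5 new eyes.

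The size is modest. These are listed among other clinical outcomes (SAP 3.3), no success criterion depends on them, and the study has at most 10 eyes. Findings absent at entry remain visible, and adverse event and acuity analyses cover part of the gap. What remains uncovered is mainly AMD progression short of a named adverse event or a 10-letter loss.

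The conclusion rests on two assumptions: that the forms do not already code findings as new or worse, and, for the ranges shown, the illustrative baseline counts. It is an inexpensive improvement to reporting; the documents do not support reading it as a failure of safety surveillance.

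**What to change.** Keep the by-visit counts in SAP 7.5.7.5 and 7.5.7.7. Add, for OCT and for fundus findings:

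> For each finding, eyes will be cross-tabulated by preoperative status and status at the visit. The number and percent of eyes that are new, unchanged or resolved will be given, and worsened where the form records grade or extent, at each scheduled visit and cumulatively through 12 months. The denominator is eyes examined both preoperatively and at that visit; for the cumulative summary, eyes examined preoperatively and at least once afterwards. Every eye with a new or worsened finding will be listed.

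The same table may be added for slit lamp. Gonioscopy has no preoperative examination and stays as by-visit counts.

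The cost is two extra tables and a listing of at most 10 eyes, with no added visit or procedure. If the forms do not grade findings, a better/same/worse entry would be needed to fill the worsened category. Without it, the table still gives exact counts of new and resolved findings. Specifying this now also keeps it out of the post hoc category that SAP 6.1 assigns to analyses not described in the plan.

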# 7.5.7.8 Specular Microscopy

Endothelial cell count and its change from baseline will be summarized descriptively at each visit.

## 7.5.7.9 Visual Symptoms

Each item of the Visual Function Questionnaire (VFQ-25) will re-coded and a score calculated according to the NEI VFQ-25 Scoring Algorithm, for each subject at each specified visit. These scores will be summarized based on mean, standard deviation, minimum, and maximum. Similar descriptive statistics will be prepared for the change in the VFQ-25 from preoperative.

# 7.5.7.10 Surgical Difficulty

The distribution of responses to surgical difficulty and managing of the capsular tissue will be summarized at the operative visit by number and percentages of eyes.

#### 8 CHANGES FROM PLANNED ANALYSES

# 8.1 Changes from the Original Protocol

Version 1.1 – Added safety analyses for surgical difficulty.

Version 1.2 – Updated endpoint analyses and clinical assessments to reflect revision 4 of the clinical protocol.

Version 1.3 – Added secondary effectiveness endpoints (UCNVA at 12 months compared to BCNVA at baseline and BCNVA at 12 months compared to baseline); added safety endpoint for SSIs.

